### **3. Study Populations**

Inclusion and exclusion criteria are sometimes modified during the duration of the protocol. Before beginning analysis, the statistical team will review the criteria in the SAP to confirm it is up to date with the current criteria.

#### **a. Eligible Patients**

1. The study population will consist of women with newly diagnosed ovarian, fallopian tube, or primary peritoneal cancer and no previous treatment.
2. A retrospective cohort of women with ovarian, fallopian tube, or primary peritoneal cancer and low serum 25(OH)D that did not receive repletion identified from available tumor bank serum samples.

#### **b. Inclusion Criteria**

1. Patients must have a histologic diagnosis of ovarian, fallopian tube, or primary peritoneal carcinoma per pre-treatment biopsies by laparoscopy, or interventional radiology, paracentesis, or CT guided core biopsy. Histologic documentation of the original primary tumor is required via the pathology report.
2. Patients must have adequate:
  1. Renal function: Glomerular Filtration Rate (GFR)  $\geq 30$ .
  2. Gastrointestinal absorption: No underlying malabsorption syndrome (i.e. inflammatory bowel disease, celiac disease)
  3. Ability to tolerate oral medication.
3. Patients taking vitamin D at the time of enrollment without a diagnosis of vitamin D deficiency.
4. Patients with childbearing potential must have a negative pregnancy test prior to the study entry and be practicing an effective form of contraception. If applicable, patients must discontinue breastfeeding prior to study entry.
5. Patients must have signed an IRB-approved informed consent and authorization permitting release of personal health information.
6. Patients must be at least 18 years old.

#### **c. Exclusion Criteria**

1. Patients with a known pre-existing diagnosis of a vitamin D deficiency.
2. Patients with renal disease and a GFR < 30.
3. Patients with primary hyperparathyroidism.
4. Patients with other invasive malignancies, with the exception of nonmelanoma skin cancer. Patients with concomitant endometrial cancer diagnosed at the time of their ovarian cancer are allowed to participate if the endometrial cancer is FIGO stage IB or less.
5. Patients of childbearing potential, not practicing adequate contraception, patients who are pregnant, or patients who are breastfeeding are not eligible for this trial.

#### 4. Analysis Populations

The analysis populations are defined as below.

- **Safety population:** All patients who receive at least one dose of vitamin D will be included in the analyses of compliance and safety.
- **Evaluable population:** For tumor response analysis, the evaluable population will comprise all patients who have sufficient baseline and on-study measurements of tumor response parameters.

#### 5. Summary of Study Population

##### a. Patient Disposition

1. Demographic, clinical, and disease characteristics and outcomes will be collected from all patients prospectively. Descriptive statistics will be used to summarize the demographic and clinical characteristics of patients. Chi-square and t-tests will be used to make comparisons between groups.
2. The association between serum leptin and 25(OH)D levels will be compared among groups, including any change in leptin levels observed in the vitamin D supplementation group. Because there is a positive linear association between BMI and serum leptin levels, BMI will be corrected for during analysis for -potential relationships between serum leptin and 25(OH)D.

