referred to a primary care physician for further management. Data collection will continue for 1 year or until the time of disease recurrence. Patient's will no longer have data collected after obtaining serum 25(OH)D and leptin levels at the time of recurrence. A retrospective cohort of women with low serum 25(OH)D that did not receive repletion of vitamin D will be used as a control group for comparison. This control group will be identified from available tumor bank serum samples including those previously identified in the above-mentioned unpublished study at the University of Oklahoma. These samples will be used to evaluate serum levels of 25(OH)D, leptin, and evaluate Buffycots VDR SNP polymorphism for *FokI*.

Cohort	Therapy
1 (Normal 25(OH)D)	None
2 (Low 25(OH)D (<20ng/mL)	50,000 IU cholecalciferol weekly for 8 weeks followed by 2,000 IU daily thereafter

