8.0 Study Parameters

8.1 Observations and Tests

The following observations and tests are to be performed and recorded on the appropriate form(s).

Observation and Tests	Screening	At each treatment visit	Completion of primary therapy	6 months after therapy completion	Time of recurrence or 1 year surveillance (if no recurrence)
History & Physical	1	X	X	X	X
Vital Signs and Weight	1				
Toxicity assessment	1	X	X	X	
Serum 25(OH)D	1		X	X	X
Serum Leptin	1		X	X	X

Serum Cr (and GFR)	1				
Red top and Purple topped blood tubes (for VDR SNP analysis)	1				
Serum pregnancy test (if potential exists)	1				

1. Must be obtained within 21 days prior to initiating protocol therapy.

All other blood draws (end of treatment, 6 months after therapy completion, Time of recurrence or 1 year surveillance) must occur within 8 weeks of expected date.

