### b. Sample Size and Power

The anticipated enrollment is 100 patients based on estimated new diagnoses of ovarian cancer treated in the Division of Gynecologic Oncology annually at the Stephenson Cancer Center. Based on the previously mentioned unpublished data, we presume that at least 25 of the prospectively enrolled patients will be vitamin D deficient. All of the vitamin D deficient women will be repleted with oral vitamin D. We will compare outcomes between these patients

and 75 vitamin D deficient ovarian cancer patients from previous years (these will include patients from the above-mentioned previous retrospective review as well as other patients with banked blood samples) using logistic regression. We will control for age, stage, and histology. With 25 prospective patients and 75 retrospective patients we will have 80% power to detect differences of 32% in chemotherapy delay between ovarian patients who were not vitamin D deficient (33%) and who were vitamin D deficient (65%).

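### Outcomes are said to be collected prospectively from all patients, but the 75 unrepleted controls are retrospective and the plan does not say how their morbidity is obtained, so data source coincides with arm

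*SAP*

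**What the plan says.** SAP section 5a, on patient disposition, says: "Demographic, clinical, and disease characteristics and outcomes will be collected from all patients prospectively". The same sentence stands in Protocol 3.0, in a paragraph about the follow-up of enrolled women.

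The control group is described differently. Protocol 3.0: "A retrospective cohort of women with low serum 25(OH)D that did not receive repletion of vitamin D will be used as a control group". SAP section 3a lists it as a separate eligible group: "A retrospective cohort of women with ovarian, fallopian tube, or primary peritoneal cancer and low serum 25(OH)D that did not receive repletion". SAP section 2b counts "75 vitamin D deficient ovarian cancer patients from previous years" and gives their origin: "these will include patients from the above-mentioned previous retrospective review as well as other patients with banked blood samples".

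For enrolled women, the Protocol 8.1 schedule has a row "Toxicity assessment" marked at screening, each treatment visit, completion of primary therapy and 6 months afterwards. Protocol 13.1 adds an electronic case report form, and SAP section 8 adds investigator grading by CTCAE version 4. For the controls, Protocol 3.0 says which assays will be run on the stored samples (25(OH)D, leptin, *FokI*). Neither document names a source, form, definition, time window or grading rule for their morbidity outcomes.

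SAP section 6 compares morbidity across groups by chi-square. SAP section 2b plans logistic regression controlling for age, stage and histology. Neither mentions where the data come from.

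**The concern.** The primary objective contrasts deficient women who were and were not repleted. Every repleted woman is followed within the study, and every unrepleted woman is historical. If events are looked for or recorded more completely in one source than in the other, that difference appears in the analysis as an effect of vitamin D. Source and arm are the same variable here, so no covariate can separate them. Age, stage and histology describe the patient, not how her outcomes were recorded. The problem has to be dealt with when the data are collected, and the rule has to be written before abstraction begins.

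**Working it through.** **Inputs from the documents**

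- Group sizes, SAP 2b: "With 25 prospective patients and 75 retrospective patients we will have 80% power to detect differences of 32% in chemotherapy delay". The total is 25 + 75 = 100, and the historical share is 75/100 = 75%, all in one arm. This 100 is not the anticipated prospective enrolment, which happens also to be 100.
- Delay rates, SAP 2b: 33% and 65%. The SAP attaches them to non-deficient and deficient women; here 33% is used for the repleted arm and 65% for the controls.
- Adjustment, SAP 2b: age, stage, histology.

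**Assumptions (not in the documents)**

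- Two-sided alpha of 0.05.
- Capture of 70-90% in the less complete source and 100% in the other.
- 65% as the true rate in both arms when there is no effect. It is the plan's delay rate and stands in for morbidity rates that the plan does not give.

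**Step 1: reproduce the plan's power.** With a pooled-variance normal approximation:

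- Pooled rate = (25 × 0.33 + 75 × 0.65)/100 = 0.57
- SE under no difference = √[0.57 × 0.43 × (1/25 + 1/75)] = 0.1143
- SE under the alternative = √[0.33 × 0.67/25 + 0.65 × 0.35/75] = 0.1090
- Power = Φ[(0.32 − 1.96 × 0.1143)/0.1090] = Φ(0.88) = 81.1%

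This agrees with the stated 80%. The power figure is not in question on this point.

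**Step 2: the two data streams side by side**

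| | Repleted (about 25) | Unrepleted (75) |
|---|---|---|
| Period | enrolled in the study | previous years |
| Outcome collection | prospective | not stated; only existing records are possible |
| Toxicity assessment | scheduled (Protocol 8.1) | no study visits |
| Delay definition for the endpoint | not stated | not stated |

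The ≥7-day threshold for delay appears only in Protocol 2.2, as part of the background study.

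**Step 3: illustrate what unequal capture would do.** False difference = true rate × (1 − capture). With 65% in both arms this gives 0.65 × 0.10 = 6.5 points to 0.65 × 0.30 = 19.5 points. The power formula of step 1 then gives, with full capture in the prospective arm:

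| Capture in control records | Observed control rate | False difference if no effect | Chance of a significant false excess in the repleted arm | Power if truth is 33% vs 65% |
|---|---|---|---|---|
| 100% | 65.0% | 0 | 2.5% | 81.1% |
| 90% | 58.5% | 6.5 points | 7.9% | 60.4% |
| 80% | 52.0% | 13.0 points | 19.7% | 37.2% |
| 70% | 45.5% | 19.5 points | 38.9% | 18.5% |

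**Step 4: reverse the assumption.** If the prospective arm captured 90, 80 or 70% and the control records captured everything, the repleted arm would look better by the same 6.5, 13.0 or 19.5 points. The chance of a significant false benefit would be 8.8, 21.5 or 40.8%.

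These figures show only how sensitive a 25-versus-75 comparison is to unequal capture. They do not estimate the bias in this trial.

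**The case against.** The strongest reply is that the SAP sentence is a carry-over. In Protocol 3.0 it sits among follow-up visits for enrolled women, and the historical cohort is introduced separately. The SAP itself calls the controls retrospective. On that reading the words cover enrolled women only and nothing is misstated. This is probably what was meant, so a reader should not infer that the SAP knowingly makes a false claim about three quarters of the comparison. But the SAP does not set that limit, and if it did, the plan would have no outcome-collection method for the 75 controls. The point stands on either reading.

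The second reply is that the documents do not show elicited toxicity entering the between-cohort comparison. SAP section 6 holds treatment-related morbidity and section 8 holds adverse events, and the safety population is limited to women who took vitamin D. Protocol 8.1 has no dedicated 30-day postoperative visit. Protocol 3.0 says the study does not dictate the treatment course, so routine records could serve for enrolled women too. All of this is correct. It means that unequal ascertainment is a well-founded inference from the design and has not been demonstrated. It does not remove the gap, because nothing requires a common source.

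A reader might also infer that the repleted arm will look worse and a real benefit will be hidden. More active follow-up makes that plausible, but the documents do not fix the direction, and step 4 shows the opposite case. Nor should 6.5 to 19.5 points be set against the 32-point target as though it were the expected loss. That target concerns chemotherapy delay, which dated treatment records can supply in both cohorts, and delay is the outcome least exposed to this problem.

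**Conclusion.** The point holds as a gap in the plan that leaves the primary morbidity comparison open to ascertainment bias. The documents establish three things: all 75 controls are retrospective, no method is given for obtaining their morbidity outcomes, and data source coincides with arm so that the planned adjustment cannot separate them. They establish neither the direction nor the size of any bias. The range of 6.5 to 19.5 points rests on an assumed 70-90% capture in one source, full capture in the other and a 65% true rate in both arms. Graded toxicity and 30-day surgical morbidity are more exposed than delay. The use of historical controls and the stated power are not faulted here. The matter should be settled before abstraction and needs no redesign.

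**What to change.** 1. In SAP section 5a, limit the sentence on prospective collection to prospectively enrolled women, and add a statement of how outcomes are obtained for the retrospective cohort.
2. For the between-cohort comparison, derive chemotherapy delay and 30-day surgical morbidity in both cohorts from the same type of routine record (infusion dates, operative and discharge records). Use one abstraction form, with one pre-specified definition and time window for each outcome. For delay, the ≥7 days of the background study is one candidate. Women carried over from the earlier review go on the same form.
3. Keep prospectively elicited toxicity for the study-drug safety analysis.

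Masking abstractors to cohort would be a useful addition where feasible, but the fix does not depend on it.

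The cost is abstraction of about 25 additional charts, for the repleted women; the controls' outcomes have to come from existing records in any case. Some events elicited prospectively will not be used in the between-cohort comparison.

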##### b. Study Drug Administration and Compliance

1. Pill counts at each patient visit will be utilized to document compliance with oral medication.

#### 6. Antitumor Evaluation

1. Treatment related morbidity (including 30-day postoperative surgical morbidity and chemotherapy-related morbidity) will be summarized by descriptive statistics as appropriate and compared across groups (chi-square for categorical variable).
2. Progression-Free Survival (PFS) at end of study (EOS) is defined as the time in months from first dose of the drug to the date of death or the first documented date of progression, whichever comes first. For patients who did not die and did not have progression, the PFS is censored at the last documented tumor assessment.

Survival curve for PFS will be generated using the Kaplan-Meier method. Median PFS with 95% CI will be computed.

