2.2 Vitamin D Deficiency in Cancer

Vitamin D has been well-studied due to its role in many important cellular pathways. Laboratory and observational studies suggest that it plays a role in many diseases such as autoimmune diseases, cardiovascular disease, diabetes, cancer risk and cancer survival. The correlation of low serum 25(OH)D with elevated risk for malignancy has been best studied in colorectal cancer [4]. Decreased levels of serum 25(OH)D have been correlated with increased risk of breast cancer in postmenopausal women. [5]. Women receiving chemotherapy and anti-hormonal therapy for breast cancer experience treatment-induced bone loss due to premature ovarian failure or direct cytotoxic effects of chemotherapy. This causes an increase in the osteoporosis and skeletal morbidity risk [6]. Similar effects can be estimated in ovarian cancer patients given that standard treatment requires surgical menopause as well as cytotoxic therapy in the majority of patients.

The majority of studies pertaining to vitamin D and ovarian cancer concern the association of low serum 25(OH)D with increased cancer risk. Limited study has been performed investigating the correlation of serum vitamin D and ovarian cancer prognosis or treatment-related morbidity. A study performed in Australia investigated serum 25(OH)D levels at the time of diagnosis of ovarian cancer in 670 women. They noted a significant association between higher circulating 25(OH)D concentrations and longer survival in women with ovarian cancer when adjusting for other clinical predictors of

survival [7]. Similarly, Walentowicz-Sadlecka et al. reported low serum 25(OH)D concentrations in women with ovarian cancer undergoing primary cytoreductive surgery to be associated with lower overall survival[8]. The impact of repletion of vitamin D in ovarian, primary peritoneal, or fallopian tube cancer patients has yet to be determined.

Findings from an unpublished study performed at the University of Oklahoma have shown an inverse correlation between low levels of serum vitamin D and treatment-related morbidity in women aged 65 years and older with ovarian cancer. More specifically, when comparing median serum 25(OH)D levels between patients who experienced chemotherapy delay ≥ 7 days versus those who did not, lower mean 25(OH)D levels were significantly associated with chemotherapy delays (23.6 ng/dL, n=28 no delay versus 14.6 ng/dL, n=30 delay, p=.0112). (Figure 1)[9].

[figure not shown]

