3.0 Study Design

This study will contain 2 cohorts, those with normal serum 25(OH)D and those with low serum 25(OH)D at enrollment. The study will take place in women with ovarian, primary peritoneal, and fallopian tube cancer, subsequently referred to as ovarian cancer in this document due to the overlap in disease and treatment.

Patients who have given written consent to enroll in the study will have a serum 25(OH)D drawn in a gold-topped tube (1 to 5mL volume) at time of enrollment and prior to initiation of treatment for their cancer. Serum 25(OH)D levels will be analyzed per laboratory protocol in our University CLIA certified lab. Blood will also be drawn for analysis of serum leptin levels and VDR *FokI* SNP genotype. A purple-topped tube (7 to 10mL volume) and red-topped tube will be collected from prospective patients. The Stephenson Cancer Center Biospecimen Bank will process the red and purple-topped tube into plasma and Buffycoats, label them with a de-identified code and transfer them to [name] lab. The plasma

will be used to evaluate leptin by ELISA and the Buffycoats used to evaluate the *FokI* SNP using PCR. Retrospective serum specimens will be used to measure leptin.

Patients with low serum vitamin D levels, defined as <20 ng/mL, will be provided a supply of cholecalciferol (vitamin D3), 50,000 IU weekly for 8 weeks that will be dispensed in the Stephenson Cancer Center outpatient pharmacy in order to standardize therapy. They will then be provided with a prescription for 2,000 IU of cholecalciferol (vitamin D3) daily following completion of 8 weeks of therapy based on current Endocrine Society guidelines in agreement with U.S. Preventive Services Task Force recommendations [14]. Treatment with cholecalciferol will not impact initiation of treatment for ovarian cancer. Compliance with cholecalciferol repletion will be assessed with medication reconciliation at every gynecologic oncology visit.

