12.0 Statistical Methods

Upon analysis, patients will be divided into two groups: Vitamin D Deficient Women and Vitamin D Normal Women.

IRB NUMBER: 7488
IRB APPROVAL DATE: 11/23/2021

Outcomes to be analyzed include differences in demographics, clinical, and tumor characteristics between groups, and differences in treatment-related morbidity or mortality between groups, including completion of treatment and treatment delays, and survival. Both 30-day postoperative surgical morbidity and chemotherapy-related morbidity will be assessed. The ability to normalize 25(OH)D levels with oral supplementation in the vitamin D deficient group will be evaluated.

Descriptive statistics will be used to summarize the demographic and clinical characteristics of patients. Chi-square and t-tests will be used to make comparisons between groups. Survival will be estimated with Kaplan-Meier curves and Cox proportional hazards regression. The anticipated enrollment is 100 patients based on estimated new diagnoses of ovarian cancer treated in the Division of Gynecologic Oncology annually at the Stephenson Cancer Center. Based on the previously mentioned unpublished data, we presume that at least 25 of the prospectively enrolled patients will be vitamin D deficient. All of the vitamin D deficient women will be repleted with oral vitamin D. We will compare outcomes between these patients and 75 vitamin D deficient ovarian cancer patients from previous years (these will include patients from the above-mentioned previous retrospective review as well as other patients with banked blood samples) using logistic regression. We will control for age, stage, and histology. With 25 prospective patients and 75 retrospective patients we will have 80% power to detect differences of 32% in chemotherapy delay between ovarian patients who were not vitamin D deficient (33%) and who were vitamin D deficient (65%).

Additionally, the association between serum leptin and 25(OH)D levels will be compared among groups, including any change in leptin levels observed in the vitamin D supplementation group. Because there is a positive linear association between BMI and serum leptin levels, BMI will be corrected for during analysis for potential relationships between serum leptin and 25(OH)D.

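### SAP section 6 gives the primary morbidity endpoint only an unadjusted chi-square across unnamed groups; the adjusted regression of SAP section 2b should be named as the primary analysis

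*SAP*

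**What the plan says.** The primary objective (Protocol 1.2.1.1; SAP 1a) concerns women deficient at diagnosis and contrasts those repleted with those not repleted. The unrepleted group is a retrospective tumour-bank cohort, "including those previously identified in the above-mentioned unpublished study at the University of Oklahoma" (Protocol 3.0). That study related 25(OH)D to "treatment-related morbidity in women aged 65 years and older with ovarian cancer" (Protocol 2.2).

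The SAP refers to the analysis of this endpoint in two places:

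- Section 6, item 1: treatment-related morbidity "will be summarized by descriptive statistics as appropriate and compared across groups (chi-square for categorical variable"). No groups, model or covariates are named.
- Section 2b, under Sample Size and Power: outcomes of 25 repleted prospective women are compared with those of 75 deficient women from earlier years by logistic regression. "We will control for age, stage, and histology".

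Protocol 12.0 contains both elements: chi-square and t-tests for group comparisons, and the same adjusted regression. SAP sections 5 to 9 do not refer back to the regression. Neither document ranks the two methods.

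On a second contrast, Protocol 12.0 opens by saying that "patients will be divided into two groups: Vitamin D Deficient Women and Vitamin D Normal Women", and lists morbidity, treatment delay and survival as outcomes to compare between them. The same section states: "All of the vitamin D deficient women will be repleted with oral vitamin D".

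**The concern.** An analyst who follows SAP section 6 as written would report a crude chi-square for the primary morbidity endpoint, and the plan would not have told them otherwise. With both methods in the documents and neither ranked, the choice could also be made after the data are seen.

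The choice matters because the comparison is with historical, non-randomised controls. Some of them were 65 or older by design of the earlier study. Prospective women enter from age 18 (Protocol 4.2.6), and Protocol 2.1 gives a median age at diagnosis of 63 and links older age to more treatment toxicity. If the controls are older on average, they would be expected to have more delays whatever repletion does, and a crude test would credit that difference to repletion.

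The second matter is one of interpretation. If Deficient and Normal in Protocol 12.0 are the two prospective cohorts, every deficient woman in that comparison has been treated. A null result could then mean that low 25(OH)D does not matter, or that repletion worked. Hypothesis 1.1.1, that low 25(OH)D goes with more morbidity, has no contrast assigned to it.

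**Working it through.** **Inputs.** From SAP 2b and Protocol 12.0: 25 prospective and 75 retrospective women; delay rates of 33% and 65%; stated power of 80%. Not in the documents: the significance level (two-sided 0.05 assumed) and any difference in delay between historical and prospective women that is not due to repletion (0 to 15 points assumed).

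**Formula.** Two-proportion test with pooled variance. p̄ = (n₁p₁ + n₂p₂)/(n₁ + n₂); SE₀ = √[p̄(1 − p̄)(1/n₁ + 1/n₂)]; SE₁ = √[p₁(1 − p₁)/n₁ + p₂(1 − p₂)/n₂]; probability of significance in the stated direction = Φ[(d − 1.96·SE₀)/SE₁], where d is the difference.

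**Step 1, the plan's own figure.** p̄ = (25 × 0.33 + 75 × 0.65)/100 = 0.57; SE₀ = 0.1143; SE₁ = 0.1090; power = Φ[(0.32 − 0.2240)/0.1090] = Φ(0.88) = 0.811. Exact enumeration of the uncorrected chi-square gives 0.821. The stated 80% is reproduced as an unadjusted comparison, so it matches the chi-square and makes no allowance for covariates. It also puts repleted women at the rate of women who were never deficient.

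**Step 2, crude test when repletion has no effect.** Historical women (75) are held at 65%. Repleted women (25) are lower by d for other reasons, such as age or era.

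| d (points) | Repleted rate | p̄ | SE₀ | SE₁ | z | False finding for repletion | Exact |
|---|---|---|---|---|---|---|---|
| 0 | 65% | 0.6500 | 0.1102 | 0.1102 | −1.960 | 2.5% | 2.8% |
| 5 | 60% | 0.6375 | 0.1110 | 0.1124 | −1.491 | 6.8% | 7.2% |
| 10 | 55% | 0.6250 | 0.1118 | 0.1137 | −1.048 | 14.7% | 15.3% |
| 15 | 50% | 0.6125 | 0.1125 | 0.1142 | −0.618 | 26.8% | 27.7% |

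**Step 3, whether adjustment helps.** This is an illustration on assumptions outside the documents: 1,000 simulated trials per scenario, historical women shifted by 0.5 to 1 SD in one prognostic covariate, and a log-odds effect of 0.5 to 0.8 per SD. With no repletion effect, the crude chi-square rejected (either direction) in 7% to 36% of trials and the adjusted regression in about 4% to 6%. Over all scenarios, including those with no shift or no covariate effect, adjusted power under 33% versus 65% was about 67% to 80%. Some fits gave convergence warnings, so these figures are approximate. The simulation contains no era effect, which adjustment for age, stage and histology would not remove.

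**Step 4, room for the model.** Women without a delay number 100 − (25p + 75 × 0.65). That is 35 if the repleted rate p is 65% and 43 if it is 33%. With 4 to 5 model terms (assumed), this is 35/5 = 7 to 43/4 ≈ 11 per term. The model fits only if stage and histology have few categories.

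**Step 5, the Deficient-versus-Normal contrast.** Protocol 3.0 says "This study will contain 2 cohorts, those with normal serum 25(OH)D and those with low serum 25(OH)D at enrollment", and Protocol 12.0 adds that "The ability to normalize 25(OH)D levels with oral supplementation in the vitamin D deficient group will be evaluated". Both point to the prospective cohorts. Take 25 deficient women at 0.65 − 0.32f against 75 normal women at 0.33, where f is the share of the 32-point gap that repletion closes (assumed). For f = 0, 0.25, 0.50, 0.75 and 1, the two-sided rejection probability is 81%, 57%, 30%, 12% and 5%. The last figure is simply the type I error.

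**The case against.** The strongest reply is that the plan already commits to the adjusted analysis. SAP 2b names the two groups, the method and the covariates, and Protocol 12.0 repeats them in its methods section. On that view only a cross-reference is missing, and the 7% to 27% describes an error that occurs only if the analyst ignores section 2b. Much of this stands. A reader might infer that the SAP has no adjusted analysis, or that the two documents contradict each other; neither is so. What remains is that the SAP section analysing the endpoint gives a different, unadjusted method, and nothing says which one decides.

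The age argument also has limits. The controls include other women with banked samples, for whom no age restriction is stated. In the earlier study's delay comparison (58 women), the 28 without delay had a median of 23.6, so at least 14 were above the cut-off of 20 if the printed values are read in ng/mL. At most 58 − 14 = 44 of those women could be deficient, which leaves at least 75 − 44 = 31 controls from elsewhere if these 58 are all that study supplies. The age mix of the 75 is therefore unknown.

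On the second contrast, hypothesis 1.1.1 is not the primary objective, and the plan nowhere says that a null result would refute it. Protocol 12.0 does not use the word prospective for these two groups, so that reading is an inference. The alternative, pooling the historical women into the deficient group, would mix repleted and unrepleted women and be no clearer. Loss of contrast occurs only if repletion works. It may be smaller for early events such as surgical morbidity, since weekly repletion runs for eight weeks and does not hold up cancer treatment.

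**Conclusion.** The point holds as a gap in the SAP. The primary morbidity endpoint has an unadjusted test in the section that analyses it and an adjusted model in the sample-size section, with no statement of priority. If the crude test were used and non-repletion differences raised historical delay by 5 to 15 points, a false finding for repletion would occur in about 7% to 27% of trials instead of 2.5%. These figures assume two-sided 0.05 and the plan's 65% delay rate, and they apply to chemotherapy delay only.

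A reader might conclude that the trial will be biased in favour of repletion by such an amount. The documents do not support that: they give neither the size of any difference nor the age mix of the controls, and the model that would limit the age, stage and histology part is already planned. A reader might also conclude that the Deficient-versus-Normal comparison is invalid, or that hypothesis 1.1.1 calls for a new comparison of historical deficient with prospective normal women. The first goes too far, because the comparison is only harder to interpret to the extent that repletion works. The second would mix deficiency with era and age, and is not recommended here.

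**What to change.** 1. In SAP section 6, item 1, state that the primary morbidity analysis is the section 2b logistic regression of repleted prospective versus unrepleted historical deficient women, adjusted for age, stage and histology. State that chi-square results are descriptive only.
2. In the same place, fix a small number of categories for stage and histology, and note that era differences remain after adjustment.
3. In Protocol 12.0, add one sentence: the Deficient-versus-Normal comparison sets treated deficient women against normal women, is not the primary contrast, and a null result does not refute hypothesis 1.1.1.

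The cost is wording, with no new patients, samples or analyses. The drawbacks are that adjusted power may fall below the stated 80% if the groups differ in age, stage or histology, and that conclusions will be more cautious.
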